#### 1 SYNOPSIS

#### Name of Sponsor/Company: Privo Technologies

#### Name of Finished Product: PRV111 (Cisplatin Transmucosal System)

#### Name of Active Ingredient: Cisplatin

**Title of Study:** Phase 1/2, Open-Label, Single-Arm, Safety and Efficacy Dose-Finding, Systemic Exposure, and Device Technical Effects of PRV111 (Cisplatin Transmucosal System) in Subjects with Oral Squamous Cell Carcinoma

**Phase of Development:** Phase 1/2

#### **Objectives:**

#### **Primary Objectives**

• Determine a safe and efficacious dose of PRV111 (Cisplatin Transmucosal System) (cisplatin drug-loaded patch + permeation enhancer [PE]) under the conditions of the trial.

#### Secondary Objectives

- Evaluate tumor response
- Assess the safety and tolerability of the treatment
- Evaluate systemic, tumor and lymph node (if available) platinum levels following administration
- Evaluate device technical success including the residual cisplatin level in the patch after the application period

**Methodology:** This is a Phase 1/2, open-label, prospective, single-arm study of the safety and efficacy dose-finding, systemic exposure, and device technical success of PRV111 (Cisplatin Transmucosal System) (cisplatin drug-loaded patch+PE) in subjects with oral squamous cell carcinoma (SCC) amenable to surgery.

*Study Design:* This is a 2-stage adaptive study. For Stage 1, up to 10 subjects will be enrolled for the purpose of 5 evaluable subjects for the 1st stage of the study to determine a safe and efficacious dose. For Stage 2, the target goal is 11 evaluable subjects for the efficacy analysis of the final dose. If the dose remains the same as Stage 1, Stage 2 will target 6 additional evaluable subjects but up to 21 subjects will be recruited if the dose is changed between Stage 1 and 2.

For the purpose of dose selection, tolerable dose is defined as a dose where fewer than 33% of subjects being evaluated within the safety population present with dose-limiting toxicities (DLTs). Effective dose is determined based on the evaluable population as described in the Statistical Methods section.

The 2 stages of the study are described below:

**Stage 1:** Up to 10 subjects will be enrolled for the purpose of 5 evaluable subjects and undergo 3 treatment applications at each of the 4 planned treatment visits. Each treatment visit will include 1 ml of the PE which will be applied pre and post patch application (see Pharmacy Manual for details). Starting approximately 5 minutes after application of the PE, 1 or 2 patches (depending on tumor size) will be applied. A total of 3 treatment applications of patches will occur. These successive applications will span approximately 35 minutes. The 3 applications provide a total of 6 mg of cisplatin per visit (12 mg if 2 patches are applied at the same time). The 4 treatment visits will be separated by 2 to 6 days (at least 48 hours apart).

The following decisions will be made based on safety and efficacy of the dose:

#### **Dosing Rules for Stage 1:**

- 1) If fewer than 2 subjects experience DLTs, then the following scheme will be considered for stage 2 dosing:
  - a. If fewer than or equal to 2 of the evaluable subjects have a response (Tumor volume change from baseline (CFB) expressed as percent change from baseline (PCFB) complete response [CR], strong response [SR] or partial response [PR]) the dose will be escalated from 3 to 5 treatment applications per treatment visit for Stage 2.

Confidential Property of Privo Technologies, Inc. Page 8 of 59

Name of Sponsor/Company:	Privo Technologies
	0

Name of Finished Product: PRV111 (Cisplatin Transmucosal System)

#### Name of Active Ingredient: Cisplatin

- Pathologically proven and clinically confirmed T1 (<2 cm) or T2 (>2 cm but ≤4 cm) SCC of the lip or oral cavity (anterior 2/3 of the tongue, floor of mouth, lower and upper gingiva, salivary gland, hard palate, and buccal mucosa).
- 3. Tumor must be easily accessible, with no evidence of infection or active bleeding, encroaching major vessels or clinical evidence of neural invasion. Tumors should not have been previously irradiated.
- 4. Tumor must be amenable to surgical resection no later than 42 days post Visit 1.
- 5. Clinically and/or radiologically measurable tumor.
- 6. Eastern Collaborative Oncology Group Performance Status of  $\leq 2$ .
- 7. Adequate renal function as demonstrated by renal creatinine clearance ≥50 mL/min (calculated using the Cockcroft-Gault formula).
- Adequate organ function defined as: ANC ≥1000/µL, platelet ≥100,000/µL; hemoglobin ≥9.0 g/dL; AST and ALT ≤2.5 times the upper limit of normal (ULN), serum bilirubin ≤1.5 times the ULN or direct bilirubin ≤ULN for subjects with total bilirubin >1.5 times the ULN.
- 9. Candidates for standard of care treatment consisting of surgery.
- 10. Male and female subjects of childbearing potential must agree to use 2 methods of effective contraception from screening and for at least 30 days after the final dose of investigational product. Appropriate birth control is defined as barrier methods with spermicides, oral or parenteral contraceptives and/or intrauterine devices, or naturally or surgically sterile (with documentation in the subject's medical records). Postmenopausal women are defined as presenting at least 12 months' natural spontaneous amenorrhea, or at least 6 weeks following surgical menopause (bilateral oophorectomy). Females of childbearing potential must be non-lactating and have a negative serum hCG within 14 days of treatment initiation.
- 11. Absence of any serious underlying medical conditions which could impair the ability of the subject to participate in the study.
- 12. Have a life expectancy of  $\geq$ 3 months.
- 13. Willing and able to provide written informed consent.
- 14. Able to return to study site for treatment and follow-up visits as defined in the Protocol.

#### **Criteria for Exclusion:**

An individual who meets any of the following criteria will be excluded from participation in the study:

- 1. Known distant metastasis of the SCC of the oral cavity
- 2. Systemic chemotherapy for the treatment of SCC of the head and neck less than 2 years prior to Screening
- 3. Concurrent documented malignancy, with the exception of localized SCCs of the skin
- 4. Exposure to any investigational agent within 3 months prior to Screening
- 5. Known allergy or hypersensitivity to platinum-containing agents, or known intolerance to a prior platinumcontaining agent, or to any of the excipients, which, in the judgement of the physician will preclude reexposure to platinum-containing agent
- 6. Active, uncontrolled infection requiring systemic therapy, such as but not limited to HIV, Hepatitis B or C
- 7. Uncontrolled intercurrent illness that would risk subject safety, interfere with the objectives of the Protocol, or limit subject compliance with study requirements, as determined by the Investigator
- 8. Known or suspected pregnancy, planned pregnancy, or lactation
- 9. Any medical or psychiatric condition that may compromise the ability to give written informed consent

Test Product, Dose and Mode of Administration: PRV111 (Cisplatin Transmucosal System) consists of:

• PE solution **and the second second and the second second** 

Name of Sponsor/Company: Privo Technologies

Name of Finished Product: PRV111 (Cisplatin Transmucosal System)

Name of Active Ingredient: Cisplatin

• Patch with polymeric matrix, embedded cisplatin-loaded particles (CLPs), and a non-permeable backing. Each 2 cm x 2 cm PRV111 topical patch covers a tumor region of 4 cm^2 and contains 0.5 mg/cm^2 (total 2 mg) of cisplatin.

patch(es). The number of patches used for each subject should remain consistent throughout treatment. Refer to the Pharmacy Manual for detailed instructions for use.

**Duration of Treatment:** Up to 6 weeks of treatment prior to the scheduled resection of the tumor and 6 months post-surgical follow-up. *Note:* The PRV111 treatment should not cause a delay to the scheduled surgery. Visit 1 can be performed within 42 days prior to the scheduled surgery.

#### Criteria for Evaluation: Safety/Tolerability evaluation based on:

- Adverse events
- Physical examination, vital signs, and weight
- Blood and urinary tests: complete blood count, chemistry panel, and urinalysis
- Electrocardiogram
- Oral examination: including observation for mucositis and other signs of local reaction to the test article
- Neck lymph nodes examination

#### Efficacy, based on:

- Tumor volume change from baseline clinical assessment (CR, PR, SR, SD, or PD). Response defined as CR, SR, or PR; non-response defined as SD or PD.
- Ruler or caliper measurements of tumor volume
- •
- Tumor photography and measurements
- Loco-regional control: subjects will be followed-up for disease recurrence and safety following surgery

#### Pharmacokinetics:

• Whole blood samples will be assessed for total platinum content

#### Technical Success will be defined as:

- Taste of the PE solution
- Taste of the PRV111 patch
- Adhesion, including the time of adhesion of PRV111 patch
- PRV111 patch peel-off
- Residual cisplatin level in the patch after the application period. All PRV111 patches will be assessed for the amount of residual cisplatin in each patch after each application period. If the product detaches prematurely, the residual cisplatin will be assessed and the time of detachment will be noted.

#### **Statistical Methods:**

Safety outcomes resulting in a DLT will be used during the conduct of this study to select doses being tested according to pre-defined thresholds of toxicity.

• Local and systemic safety and tolerability will be summarized using descriptive statistics. The number of subjects with DLTs will be capped to be fewer than 2 subjects with DLTs out of 5 new subjects enrolled.

The treatment regimen will be deemed tolerable if fewer than a third of the subjects exposed to it present DLTs.

#### Name of Sponsor/Company: Privo Technologies

#### Name of Finished Product: PRV111 (Cisplatin Transmucosal System)

#### Name of Active Ingredient: Cisplatin

- Efficacy based on tumor volume CFB criteria will be summarized, and the null hypothesis that the probability of response is at most 30%, where a response is the occurrence of CR, SR or PR will be tested using a 1-sided test exact binomial test at level 0.018.
- Systemic and tumor and lymph nodes (if available) platinum levels will be summarized using descriptive statistics.
- Variables measuring technical success (including residual cisplatin level in the patch) will be summarized using descriptive statistics.

All summaries will be presented by dose, as appropriate. Incidence of pre-surgery AEs will be summarized using number and percent for each System Organ Class and Preferred Term (MedDRA), including Investigator assessment of relatedness and severity grade.

All assessments will be listed and summarized using mean, standard deviation, median, minimum, and maximum for continuous variables and using number and percent for categorical assessments.

Data from this study will be summarized at 2 timepoints:

- Final report at End of Stage 2: after all subjects complete PRV111treatment, efficacy, pharmacokinetics, and technical data will be analyzed, including all available safety data from the long-term follow-up.
- Long term safety report: after all subjects complete all observations.

#### **Power and Sample Size**

In the first stage, 5 evaluable subjects will be accrued. If there are 2 or fewer responses in these 5 subjects, the dose will be escalated. Otherwise, the dose will remain the same or de-escalated based on safety data. Additional subjects will be accrued for a total of 11 evaluable subjects at the final dose.

If the dose is not increased after Stage 1, the test will be performed using all evaluable subjects from Stage 1 and 2. If the dose is adjusted after Stage 1, the test will be performed using all evaluable subjects from Stage 2.

Based on Simon's 2-stage procedure, the null hypothesis that the true response rate is 0.30 will be tested against a one-sided alternative. The null hypothesis will be rejected if 7 or more responses are observed at the final dose. This design yields a type I error rate of 0.018 and power of 96.44% when the true response rate is 0.85.

Null response rate: P 0	Alt. response rate: $P_1$	Alpha one-tailed	Power	nl	r1	Ν	R
0.30	0.85	0.018	96.44%	5	2	11	6

N is the total number of evaluable subjects at the final dose

n1 is the number of evaluable subjects accrued during Stage 1

r1, if r1 or fewer responses are observed during stage 1, escalate the dose if safety requirements are met

R, if R or fewer responses are observed by the end of Stage 2 in N subjects, then an effective dose is not found

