# 6 INVESTIGATIONAL PLAN

# 6.1 Overall Trial Design and Plan: Description

*Study Design:* This is a 2-stage adaptive study. For Stage 1, up to 10 subjects will be enrolled for the purpose of 5 evaluable subjects for the 1st stage of the study to determine a safe and efficacious dose. For Stage 2, the target goal is 11 evaluable subjects for the efficacy analysis of the final dose. If the dose remains the same as Stage 1, Stage 2 will target 6 additional evaluable subjects but up to 21 subjects will be recruited if the dose is changed between Stage 1 and 2.

For the purpose of dose selection, tolerable dose is defined as a dose where fewer than 33% of subjects being evaluated within the safety population present with DLTs. Effective dose is determined based on the evaluable population as described in the Section 10.2.

The 2 stages of the study are described below:

*Stage 1:* Up to 10 subjects will be enrolled for the purpose of 5 evaluable subjects and undergo 3 treatment applications at each of the 4 planned treatment visits. Each treatment visit will involve application of 1 ml of the permeation enhancer and will be applied pre and post patch application (see Pharmacy Manual for details) (One ml vial of PE per visit, see Pharmacy Manual). Starting approximately 5 minutes after application of the PE, 1 or 2 patches (depending on tumor size) will be applied. A total of 3 treatment applications of patches will occur. These successive applications will span approximately 35 minutes. The 3 applications provide a total of 6 mg of cisplatin per visit (12 mg if 2 patches are applied at the same time). The 4 treatment visits will be separated by 2 to 6 days (at least 48 hours apart).

The following decisions will be made based on safety and efficacy of the dose:

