#### c.

#### Figure 2. Stage 1 dose determination scheme

d) Target Dose for Stage 2a

*Stage 2:* In case of dose escalation or de-escalation, Stage 2 will be conducted in 2 parts: Stage 2a and Stage 2b.

Subjects will receive 2, 3, or 5 treatment applications at each of the 4 planned treatment visits, depending on the results of Stage 1. Up to 21 additional subjects will be enrolled in Stage 2 if necessary, for the purpose of 11 total evaluable subjects at the final dose for the efficacy analysis.

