#### Stage 2a:

This stage will include 5 subjects (Stage 2a flowcharts). In this stage, only safety outcomes will be considered for determining the dosing regimen for the set of subjects to be enrolled in Stage 2b. All subjects enrolled in this stage will be monitored for possible DLTs.

- 1) If fewer than 2 subjects with DLTs in Stage 2a, enrollment will continue for the remaining number of subjects required in Stage 2b at the same dose.
- 2) If 2 subjects experience DLTs in Stage 2a, dosing will be re-considered. It may be stopped or, when possible, decreased for the remaining subjects enrolled in Stage 2b:
  - a. If "Stage 2a Escalated Dose", the original dose will be used on the remaining patients.

b. If "Stage 2a - De-escalated Dose", the study will stop, as no safe dose could be determined.

a) Stage 2a Enrollment Goal: 5 subjects
b) 2 subjects with DLTs, evaluated based on Safety Subjects
c) Target dose for Stage 2b

Figure 3. Stage 2a safety scheme in case of escalated dose decision

Figure 4. Stage 2a safety scheme in case of de-escalated dose decision

**Stage 2b:** In this stage both safety and efficacy will be evaluated. All subjects will be monitored for possible DLTs (Stage 2b – All Doses flowchart).

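### After a dose change, the analysis-set sentences do not select the subjects at the final dose, and the stated 0.018 belongs only to the two-stage rule on the same-dose path

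*Protocol*

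**What the plan says.** - **Analysis set** (Protocol synopsis, Power and Sample Size; Protocol 10.3 note; SAP 5.1). One sentence covers a dose that does not go up: "If the dose is not increased after Stage 1, the test will be performed using all evaluable subjects from Stage 1 and 2". The sentence after it covers a dose that is altered in any direction: "If the dose is adjusted after Stage 1, the test will be performed using all evaluable subjects from Stage 2".
- **Rejection rule and N** (Protocol synopsis and 10.2). The success criterion is: "The null hypothesis will be rejected if 7 or more responses are observed at the final dose". The note under the design table defines the sample size in the same terms: "N is the total number of evaluable subjects at the final dose". The table gives n1 = 5, r1 = 2, N = 11, R = 6, one-sided alpha 0.018, and power 96.44% at a response rate of 0.85 against a null of 0.30. The text attributes these to Simon's two-stage procedure.
- **Named test** (Protocol synopsis, Statistical Methods; similarly Protocol 10.2 and SAP 5.1): the null hypothesis "will be tested using a 1-sided test exact binomial test at level 0.018". SAP 5.2.1 sets 0.018 as the level for all hypothesis tests.
- **Dose changes** (Protocol 6.1). On accrual: "up to 21 subjects will be recruited if the dose is changed between Stage 1 and 2". On when Stage 2a applies: "In case of dose escalation or de-escalation, Stage 2 will be conducted in 2 parts". If 2 subjects have DLTs in Stage 2a at the escalated dose, "the original dose will be used on the remaining patients".
- **SAP 2.2** differs. It has 6 evaluable subjects in Stage 1 de-escalation, 6 subjects in Stage 2a and 16 evaluable at the final dose. It allows up to 10 further evaluable subjects after a return to the original dose. It also has a Stage 2a branch for an unchanged dose, which the Protocol does not have.

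**The concern.** The primary claim is that one particular dose is effective. With 11 subjects and a cut-off of 7, one responder counted from the wrong dose can decide it. The set sentences sort subjects by stage and by what happened to the dose after Stage 1. The rejection rule sorts them by final dose. The two agree when the dose stays the same and need not agree otherwise.

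The plan also gives one level and one cut-off for every path. In a standard Simon design, a poor Stage 1 ends the trial. Here it leads to escalation and a second test, so the error rate of the standard rule does not describe the whole procedure.

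**Working it through.** **1. Which subjects each passage selects**

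| Branch | Set sentences | Final-dose wording |
|---|---|---|
| Same dose | Stages 1 and 2 | Stages 1 and 2: agree |
| Escalated and kept | Stage 2 | Stage 2: agree |
| Escalated, then returned | Stage 2: Stage 2a at the escalated dose plus Stage 2b at the original | Stage 1 plus Stage 2b: conflict |
| De-escalated | Not increased, so Stages 1 and 2; also adjusted, so Stage 2 only | Stage 2 only |

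On the return branch the first sentence would not help either. Pooling both stages still brings in the escalated-dose subjects from Stage 2a.

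**2. Reproducing the plan's figures** (inputs from the Protocol table)

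Formula: the sum over x = 3 to 5 of P(X1 = x | 5, p) × P(X2 ≥ 7 − x | 6, p).

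- p = 0.30: 0.1323 × 0.0705 + 0.0284 × 0.2557 + 0.0024 × 0.5798 = 0.0093 + 0.0072 + 0.0014 = **0.0180**.
- p = 0.85: 0.1382 × 0.9527 + 0.3915 × 0.9941 + 0.4437 × 0.9996 = **0.9644**.

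Both stated figures are right for this rule. The 0.0180 is a joint probability: pass Stage 1 with 3 or more of 5, then reach 7 of 11.

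**3. Single-stage test on 11 subjects**

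- P(X ≥ 7 | 11, 0.30) = 0.0216; power at 0.85 is 98.4%.
- P(X ≥ 8 | 11, 0.30) = 0.0043; power at 0.85 is 93.1%.

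A plain exact binomial test at 0.018 therefore does not reject at 7 of 11 and needs 8.

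**4. Like-for-like levels, both doses at 0.30, no DLT-driven change**

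- P(X1 ≤ 2 | 5, 0.30) = 0.8369.
- Joint probability of success through escalation: 0.8369 × 0.0216 = 0.0181.
- Either dose declared effective: 0.0180 + 0.0181 = **0.0361**.
- With 8 of 11 after the change: 0.0180 + 0.8369 × 0.0043 = 0.0216.

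**5. Return branch with the set as written**

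All figures here are conditional on entering the branch, with the original dose at 0.30.

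- Five escalated-dose plus 6 original-dose subjects, cut-off 7: 0.0216, 0.084, 0.173 or 0.367 if the escalated-dose response rate is 0.30, 0.50, 0.65 or 0.85 (assumed range).
- Three evaluable escalated-dose subjects plus 8 at the original dose: 0.050, 0.082 or 0.139 at 0.50, 0.65 or 0.85. Fewer may be evaluable because DLTs end dosing.
- Five plus 11 at the final dose, 16 in all and within the cap of 21, cut-off still 7: P(X ≥ 7 | 16, 0.30) = **0.175**, with the escalated dose also at 0.30.

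If the DLT risk is 5%, 10% or 20% at every dose and independent of response (assumed), two or more DLTs in 5 has probability 0.0226, 0.0815 or 0.2627. The chance of entering this branch is (1 − that) × 0.8369 × that = 0.018, 0.063 or 0.16.

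**The case against.** **The final-dose wording already governs.** The rejection rule counts responses at the final dose, which on its face excludes escalated-dose responders. This stands as a guide to intent, and for de-escalation it settles which reading fits. But the set sentences say expressly whom the test uses, and they say something else. A controlling principle does not remove the contradiction from the text.

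**The level contrast is not like for like.** A reader might infer from 0.018 against 0.0216 that a changed dose faces an easier test. The documents do not support that. The first figure is joint and the second is conditional on a dose change. On the joint scale, escalation gives 0.0181, almost the same as 0.0180. On the conditional scale, the same-dose error given 3 or more of 5 is 0.0180 / 0.1631 = 0.110.

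**7 of 11 need not be both a success and a failure.** A reader might infer an outright clash between the 7-response rule and the exact test. It disappears if the Stage 1 gate is part of the test, as the reference to Simon's procedure suggests. What stands is that the named test does not say so.

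**No error control across doses was promised.** This is correct: the plan claims 0.018 for the two-stage rule only. The 0.036 is a property that should be disclosed, not a broken commitment.

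**The return branch is uncommon.** This also stands. Multiplying the 5-plus-6 rates at 0.50 to 0.85 by the entry probabilities gives about 0.0015 to 0.007 at 5% DLT risk and 0.014 to 0.060 at 20%.

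**Conclusion.** The analysis-set sentences are wrong as written for dose-change branches. On return to the original dose they select a mixed-dose set and omit Stage 1 subjects at the final dose. On de-escalation both sentences apply, and only the Stage 2 reading fits the final-dose wording. This conclusion rests on the text alone and needs no assumed rates.

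The stated 0.018 and 96.44% are correct, but only for the same-dose two-stage rule. Given a dose change and 11 new subjects, the level is 0.0216. The either-dose figure of 0.036 assumes a 30% response rate at both doses, no DLT-driven change, exactly 11 subjects tested and cut-off 7. It should not be read as a general ceiling, because a mixed 16 with cut-off 7 gives 0.175 within the return branch. The mixed-set rates at other response rates are illustrative, and the point does not depend on them.

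**What to change.** Replace both sentences, wherever they occur, with: *The primary test uses all evaluable subjects treated at the final dose, whichever stage they entered, and no others.* Say how a subject whose regimen is reduced under Protocol 8.3 is classed. Then add a short table by branch:

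- **Same dose:** the Simon rule (3 or more of 5, then 7 or more of 11), level 0.018, stated not to be a single-stage exact test.
- **11 new subjects after a dose change:** 7 of 11, level 0.022, with the either-dose error of 0.036 disclosed. Alternatively 8 of 11, level 0.004, power 93.1%, either-dose error 0.022.
- **Return to the original dose:** state the number tested at that dose, the cut-off and the level. One example is Stage 1 plus 6 new subjects with 7 of 11. Stage 1 results of 2 or fewer add 0.0036, so the combined level for that dose is 0.0180 + 0.0036 = 0.0216.

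Reconcile SAP 2.2 (6 in Stage 1, 16 at the final dose, up to 10 additional, the unchanged-dose Stage 2a branch) with the Protocol's n1 = 5 and N = 11. The sponsor must reconcile the dosing passages; no dose or clinical rule is proposed here.

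**Cost:** wording in the Protocol synopsis, 10.2 and 10.3 note and in SAP 2.2, 5.1 and 5.2.1, plus the table. No subjects are added on the same-dose or changed-dose paths. Choosing 8 of 11 costs 98.4 − 93.1 = 5.3 points of power. In the return example, success is impossible after 0 of 5 in Stage 1. At a true rate of 0.85 it has probability 0.38 after 1 of 5 and 0.78 after 2 of 5.
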